#### **Total number of participants:**

*Part A, Group 1: Up to 40 adolescent patients who meet inclusion/do not meet exclusion criteria. Patient participants will be enrolled on Part A (up to a max of 40 patient participants) until 20 patient participants enroll on Part B.*

*Part A, Group 2: Up to 40 parents/guardians of adolescent patients in Group 1. The number of Group 2 participants will be determined by the number of Group 1 participants. Only one parent/guardian per Group 1 participant will be enrolled.*

*Part B, We anticipate enrolling up to 20 patients in Part B of the study.*

#### *Total Duration of Participation in Part B*

Up to 18 months.

#### **Recruitment Methods:**

Potential participants will be recruited from Children's Healthcare of Atlanta (Egleston, Scottish Rite and Hughes Spalding locations).

Pre-screening of potential study participants who seek care at CHOA will be done using medical record review. We may also identify patients from the existing SCD clinical database maintained by [name] to identify patients with frequent healthcare utilization for pain or those who potentially may have chronic pain identified through clinical care or prior/ongoing other research studies. This is to limit burden of approaching those patients who are likely to not meet criteria for chronic pain. Participants may also be referred to the study by their treating healthcare providers. If medical records or healthcare provider report/database indicate a possible diagnosis of chronic pain, a research team member will approach the patient/parent to introduce the study and also determine if patient meets eligibility criteria. Patients may be approached for the study either in the inpatient or the outpatient setting. The study staff may also introduce the study in person-or over the telephone to discuss patient interest in the study. If eligible, and the individual is interested, the consent will be reviewed, including expected study activities, and

potential risks and benefits. A copy of the consent may be provided for review based on patient and family preference, either in person or e-mailed/mailed to the potential participant, if so requested. The individual will have an opportunity to discuss it with significant others, including caregivers and other family. The individual will also be given the opportunity to discuss it with his/her hematologist or healthcare provider, if they wish to. This may be done in-person or if the family wishes to, due to time constraints at clinic or hospital visits, over the telephone. Once a potential participant has reviewed consent and all questions have been answered, consent will be obtained in-person.

Specific attention will be given during the consenting process for the potential for increased discomfort and/or pain as a result of the yoga poses. These may result in increased use of medication, or potentially a ED visit, or hospitalization.

All questions will be answered by a member of the research team and/or the PI. If the individual agrees to participate, he/she will be consented/assented in person. A copy of the signed consent will be given to the participant.

Participants will be consented for Part A and Part B separately. For those who are enrolled in part B of the study, investigators will confirm that patients don't have exclusion criteria prior to proceeding with the first yoga session.

Flyers may be posted in the sickle cell clinics and at community sites, or in on-line patient forums, with study coordinator contact information.

#### **Monitoring of Potential adverse outcomes:**

**Pain:** There is a potential for increased discomfort and/or pain as a result of the yoga poses, even though the program is designed to be gentle. The potential for increased pain will be discussed with the participant during the consenting session and if needed, prior to each in-person yoga session, so the patient and their family are fully informed of the potential risks. Pain may result in increased use of medication, or potentially a ED visit, or hospitalization. We will also track healthcare utilization for pain, and if  $\geq 30\%$  of participants present with increased pain resulting in an ED visit or hospitalization, we will halt yoga sessions and reassess if any changes need to be made to the protocol. Since participants have chronic pain, it may be difficult to determine if the yoga program was the cause of increased pain, so we will go by patient self-report to determine if yoga program was believed to be causative. If this is the case, the participant may opt to discontinue the research study or a physician researcher may opt to withdraw the participant. We also anticipate that those who perceive an increase in pain following the program will self-discontinue from the study. Monitoring during yoga sessions will make every effort to ensure participants do not exceed their limitations.

**Other risks:** There is a possibility of muscle strain, of aggravation of an existing injury, which may cause discomfort or pain, increased medication use, need for medical treatment, increased time off work or school, or financial loss.

As with all research studies, there is also a risk of loss of confidentiality of participant data.

#### **Anticipated results and Potential problems, alternate strategies:**

We may encounter difficulties with enrollment of participants. Participants may be uninterested in complementary therapies or may believe that they may not help with chronic pain. They may not want to pursue yoga as a complementary therapy due to concerns that this may be in

conflict with their religious beliefs. There may be cultural barriers to acceptability of yoga. The yoga instructors or investigators, who are familiar with addressing concerns about yoga, will be available to answer any questions they may have about the practice of yoga itself and if potential participants have any concerns regarding yoga as a spiritual practice.

Once enrolled in Part A, participants may not complete survey, though we expect that this non completion rate will be low. Once enrolled on part B, participants may decide not to participate further in the study, or may have a medical complication between enrollment and participation in the yoga sessions that may not allow them to participate in the study. Participants may not attend one or more in-person yoga sessions. We will attempt to determine the causes for individuals dropping out of the program.

There may also be discontinuation of the program due to increased pain, or perceived increased pain, and this will also be noted as a reason for discontinuation. Systematic reviews have not shown increased risk of severe adverse events by the use of yoga in the management of chronic pain syndromes. In addition, there may be changes in health status that may prevent safe continuation of the yoga program. These aims will generate critical data on the feasibility acceptability, reach and maintenance of yoga in adolescents with SCD and chronic pain.

### **Analytic Methods:**

Part A: Descriptive statistics will be used to determine the proportion of patients with chronic pain who are willing to consider yoga and participate in a yoga program. We will also determine predictors of acceptability of yoga such as, but not limited to, age, gender, pain phenotypes, medical comorbidities, attitudes towards complementary therapies, fear of movement and pain catastrophizing. There may be additional analyses that may be conducted once these are completed.

Part B: This aim will also determine the feasibility of attendance at in-person yoga program, and safety. As in part A, we anticipate descriptive statistics will be utilized, and we will look for characteristics associated with feasibility of attendance at in-person yoga sessions. Qualitative analysis will also help indicate wider issues related to acceptability of yoga and barriers to use of yoga and other complementary therapies. Qualitative analyses will also analyze participant needs for development of a yoga app.

We will monitor for adverse effects following the in-person yoga session. If the research coordinator receives reports of increased pain in participants following a yoga session, that are perceived to be related to the yoga session, then these will be recorded. We will also record any ED visits or admissions for pain that occur within 24 hours of the yoga session. We will monitor for drop out from the study due to perceived increase in pain.

Pain diary data and quality-of-life survey and PROMIS will interrogate improvement in pain, quality-of-life from the use of yoga application program. Given the pilot nature of this study, we do not expect we will be adequately powered to detect differences in health outcomes like pain intensity and pain interference or psychological factors between pre- and post treatment values. There may be additional analyses that may be conducted once these primary analyses are completed.

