- vi. Proposed Yoga protocol (45-60 minutes), but this may be modified as yoga instructor deems necessary to suit patients with SCD. The sequence below is only to serve as a guide, and only lists representative elements, and instructor may move around the order. The final yoga protocol may be modified in-real time per instructor discretion, and to maintain safety, based on ongoing feedback and response to classes. It is possible that some elements of the yoga sessions may change as classes progress.

- a) Opening and Pranayama (breathing exercises)
  - b) Gentle warm up
  - c) Predefined set of standing and poses
  - d) Surya (Sun), Chandra (Moon) and earth series of poses
  - e) Pranayama (Breathing exercises)
  - f) Guided relaxation or 'yoga nidra'
- vii. During, and at the end of each session, feedback will be obtained from participants as a group, and will be recorded. Future yoga sessions may be modified as necessary based on participant feedback.
- viii. Email or phone reminders for upcoming yoga sessions will be sent to participants at the email address/phone numbers provided. If participants miss or are unable to attend sessions, study staff may follow up to attempt to determine reason for non-attendance.
- ix. Study staff will also record ED visit or hospitalization that occurred in the 24 hours following the yoga session. This will be assessed 24 hours after, but prior to the start of the subsequent session.

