- 4- Pain diary (2 assessments, pre and post): Participants will complete a multi-dimensional pain diary (MDP diary) for up to one week prior to and following the period of in-person yoga sessions. The pain diary is accessible via a password protected website, which is also currently used to collect pain data for other large clinical trials in SCD. Data entry will occur two times per day, morning and evening and will take less than 3 minutes to fill out at each time point. The diary can be completed up to 4 weeks prior to the anticipated start of the yoga program, and may be started up to 4 weeks following the completion of the last yoga session.

- 5- We will also obtain demographic information from patient/family including but not limited to age, sex, race, ethnicity, family income, insurance status, parent and child education status, family composition and parent marital status, religious affiliation, availability of transportation and distance from the proposed yoga site. As with Part A, if participants indicate they have previously practiced yoga, we will also gather the following: number of months/years' yoga has been practiced, frequency of practice and time of most recent practice of yoga. This would already have been gathered at the start of Part A but may be collected again if necessary.
- 6- Study staff may send email or phone reminders for completion of study assessments, and may follow up to obtain completed study assessments.
- 7- We will also follow healthcare utilization for pain during and up to 6 months after completion of the yoga program.

After the sessions have ended, and the participant has attended at least one session, all surveys will be repeated and a qualitative interview will be conducted to evaluate participant acceptability and perceived benefits/risks of yoga, as well as the perceived needs in the design of a smart-phone accessible yoga app; as described above.

The goal will be to obtain these assessments within one month prior to the planned start of Part B, and within one month of completion of the last yoga session.

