#### **COMPENSATION:**

Participants will be compensated as follows:

Part A: \$ 25 for completion of study procedures.

Part B: \$25 for completion of surveys, 2 time points = \$50

1. \$25 for qualitative interview, 1 interview = \$25
2. \$25 to cover costs of transportation and parking for each yoga session, up to 8 yoga sessions = max of \$200
3. \$1 for completion of pain diary at each time point, twice daily for 7 days X 2 time-points = max of \$28

Total possible compensation for Part B \$303.

Note that payments will be prorated based on study procedures completed.

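### Pain after a yoga session that does not lead to an ED visit or admission has no scheduled individual question behind it, so it is likely to be under-counted

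*Combined protocol and SAP*

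**What the plan says.** Safety of the program is part of Aim 1. Under Monitoring of Potential adverse outcomes the protocol states: "There is a potential for increased discomfort and/or pain as a result of the yoga poses". It adds that more medication may be needed and that causation is hard to judge in people with chronic pain, "so we will go by patient self-report to determine if yoga program was believed to be causative". Potential Risks repeats both points.

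The data collection that could serve this is as follows.

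- **Spontaneous reports** (Analytic Methods, Part B): "If the research coordinator receives reports of increased pain in participants following a yoga session", and the pain is perceived as related to the session, it is recorded.
- **Scheduled per-session check** (In-person yoga sessions, item ix): "Study staff will also record ED visit or hospitalization that occurred in the 24 hours following the yoga session". On timing: "This will be assessed 24 hours after, but prior to the start of the subsequent session". Pain itself is not part of this check.
- **Feedback** (item vii), taken during and at the end of class: "feedback will be obtained from participants as a group, and will be recorded".
- **Non-attenders** (item viii): staff may follow up to learn why a session was missed.
- **Pain diary** (Assessments, item 4): completed "for up to one week prior to and following the period of in-person yoga sessions".
- **Exit interview** (Assessments, item 2): one interview after the sessions, covering perceived harms among other topics, with a goal of completion within a month of the last session.
- **Dropout**: pain is noted as a reason for discontinuing (Anticipated results and Potential problems; Analytic Methods).

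**The concern.** The protocol makes the participant's own report the arbiter of whether yoga caused pain, but no individual participant is scheduled to be asked after a session. Whether a painful evening or next day enters the data depends largely on who speaks up. Without a fixed question and a known number of people asked, a low count cannot be told apart from a low rate of asking.

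The loss may also be selective. The monitoring section expects that people who perceive more pain will leave the study of their own accord, and Withdrawal from Study ends data collection at that point. Those most affected are therefore the most likely to miss the exit interview and the second diary. The safety team meets every 2 weeks but would have no systematic data on this harm to review.

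**Working it through.** **1. Diary coverage.** Compensation pays $1 "for completion of pain diary at each time point, twice daily for 7 days X 2 time-points". That gives 2 × 7 × 2 = 28 entries, or $28, which matches the stated maximum. The Part B total also reproduces: 50 + 25 + 200 + 28 = $303. The 28 entries span 14 days, all outside the program. Eight weekly sessions run 7 × 7 = 49 days from first to last, with no planned diary day among them. The diary may be done up to 4 weeks before the start and begun up to 4 weeks after the end, so it need not adjoin the sessions.

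**2. Scheduled questions.** With up to 20 participants and 8 sessions there are up to 20 × 8 = 160 participant-sessions. Each has a planned ED/hospitalization check. None has a planned individual pain question.

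**3. What the other routes reach.**
- In-session monitoring by a physician and the instructor ends with the class.
- Feedback at the end of a class comes before later pain from that class. Pain from the previous session could be raised at the next one, but only in a group, only by those who return, and without a set question.
- Follow-up of missed sessions is optional.
- Tracking of utilization for pain (Assessments, item 7) does not reach pain managed at home.
- Dropout tracking sees only pain bad enough to end participation.
- The interview is retrospective. Session 1 is at day 0 and session 8 at day 49, so an interview within about a month of the last session falls between day 49 and about day 80: 49/7 = 7 weeks to 80/7 ≈ 11 weeks after session 1, and less for later sessions.

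**4. Illustration of under-capture.** The documents give neither the true proportion p with yoga-related pain nor the probability c that a case is recorded; both are assumed. The number recorded among N = 20 is Binomial(20, p × c). With p = 0.30, six participants are expected. The exact one-sided 95% upper bound after 0 of 20 recorded is 1 − 0.05^(1/20) = 13.9% for the recorded rate; dividing by c gives the bound for the true rate.

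| c | Expected recorded, 20 × 0.30 × c | P(at least 6 recorded) | Upper bound on true rate after 0/20 |
|---|---|---|---|
| 1.00 | 6.0 | 0.58 | 13.9% |
| 0.75 | 4.5 | 0.28 | 18.5% |
| 0.50 | 3.0 | 0.07 | 27.8% |
| 0.25 | 1.5 | 0.003 | 55.6% |

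Over c = 0.25 to 0.75, p = 0.20 gives 1.0 to 3.0 recorded of 4 expected, and p = 0.50 gives 2.5 to 7.5 of 10.

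**5. Error in the other direction once people are asked.** If a fraction f of sessions yields a false attribution to yoga (assumed, independent across sessions), a full attender has at least one with probability 1 − (1 − f)^8. For f = 0.05 this is 1 − 0.95^8 = 34%; for f = 0.10 it is 1 − 0.90^8 = 57%.

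**The case against.** The plan does more than wait for calls. Feedback is recorded at every class, a physician is present, missed sessions may be followed up, pain-related dropout is noted, and the interview asks about perceived harms. After session 8 there are still repeat surveys, a diary and the interview, and safety meetings continue for 2 weeks. Someone who stops attending without withdrawing is still due the post-program assessments after attending at least one session. All of this stands. A reader might infer that such pain can be recorded only if it reaches the coordinator; the text does not support that. What remains is that none of these routes is a standard question put to each person after each session.

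A reader might also infer that silence will be counted as absence of yoga-related pain. The documents do not say so: they define no rate, denominator or endpoint for pain increases. Nor does the gap touch primary outcome 4, which concerns ED visits and hospitalizations within 24 hours and has its own scheduled check.

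Finally, this is a descriptive pilot of up to 20 people, and any figure for the under-count rests on assumed rates. That is correct, and it limits what can be said about size.

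**Conclusion.** The point holds as a measurement gap. Post-session pain short of an ED visit or admission is named as a risk, its attribution rests on self-report, and no scheduled individual question collects that report. The diary is silent during the program, and people who withdraw because of pain give no further data, although a reason for withdrawal is noted if offered. Under-counting is the likely direction; it is an inference from the design, not a certainty. The table illustrates how the count and the upper bound would move under assumed capture rates and does not estimate the shortfall. The change is worth making before the first session because safety is a stated aim and the remedy is small.

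**What to change.** Extend item ix of In-person yoga sessions. At the time point it already sets, and also after session 8 and for anyone who misses the next class, ask each attendee:

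1. Has pain been higher than usual since the session?
2. If so, do you believe yoga caused it?
3. Did you take extra pain medication?
4. Did you have an ED visit or admission at any hospital?

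Replace the conditional sentence in Analytic Methods with this procedure. Alongside primary outcome 4, report descriptively both the per-session proportion and the per-participant proportion with at least one self-attributed pain increase, using those asked and answering as the denominator and giving both numbers.

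There are three costs. Item ix does not say that participants are contacted; if it is met by record review, the change means up to 160 new brief contacts. The safety figure may look less favourable. Without a control group, in people with pain on 15 or more days a month, some background fluctuation will be attributed to yoga, and it accumulates in the at-least-one figure (step 5 of the working). This is why the per-session proportion is needed too; the limitation should be stated with the result.

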### **Human Subjects:**

#### *Protected Health Information*

Name, address, telephone number, and email address will be recorded to facilitate contact with study subjects, send reminders for completion of study procedures and to mail gift

cards. Medical records and PHI will be reviewed as described in this protocol. Other data gathered will include but not be limited to sickle cell genotype, type and frequency of pain medication utilization, intensity and frequency of in-patient and emergency department treatment for vaso-occlusive crisis, and co-morbidities.

If we uncover information about the participant during this study that study investigators feel believe may impact their care, they may discuss this with the participants' healthcare providers.

#### *Third Party Information*

Data Warehouse Consultants (DWC) which is an agent of Emory University that will manage the pain diary. DWC will have access to participants' phone number, email address, IP Address and data that is entered in the pain diary application.

#### *Potential Risks*

There is a risk of breach of confidentiality. All electronic data will be kept on a secure server. Paper documents will be retained in a locked file cabinet in a locked office. Consent forms will be kept separate from research data.

There is a risk of discomfort with qualitative interviews. Participants are free to refuse to answer any questions that make them feel uncomfortable. The interview may be stopped at any time.

There is a potential for increased discomfort and/or pain as a result of the yoga poses. These may result in increased use of medication, or potentially a ED visit, or hospitalization. Since participants have chronic pain, it may be difficult to determine if the yoga program was the cause of increased pain, so we will use patient self-report to determine if yoga program was believed to be causative. If this is the case, the participant may opt to discontinue the research study or a physician researcher may opt to withdraw the participant. The potential for increased pain will be discussed with the participant during the consenting session and if needed, prior to each in-person yoga session, so they and their family are fully informed of the potential risks. Medical personnel expert in sickle cell disease will be present at the yoga sessions to monitor for discomfort.

**Other risks:** There is a possibility of muscle strain, of aggravation of an existing injury, which may cause discomfort or pain, increased medication use, need for medical treatment, increased time off work or school, or financial loss.

Given the minimal risk of the pain diary, we do not anticipate concerns with its use. Participants will be consented and informed that pain data collection via MDP diary is not a means of communicating with provider but only as a reporting tool for the study. A disclaimer is present in the consent form indicating that the data collected in the study is only for reporting purposes and not as a means to inform their healthcare provider, seek or provide medical attention. Data from pain diary may be reviewed periodically, and participants may be contacted if the study team believes they have concerns. This will not be to provide medical advice but to ensure that participants have sought care for pain related or other concerns with their healthcare provider.

